8.1 Site monitoring

Before study initiation, at a site initiation visit or at an investigator's meeting, a Novartis representative will review the protocol and CRFs with the investigators and their staff. During the study, the field monitor will visit the site regularly to check the completeness of patient records, the accuracy of entries on the CRFs, the adherence to the protocol and to Good Clinical Practice, the progress of enrollment, and to ensure that the investigational treatment is being stored, dispensed, and accounted for according to specifications. Key study personnel must be available to assist the field monitor during these visits.

The investigator must maintain source documents for each patient in the study, consisting of case and visit notes (hospital or clinic medical records) containing demographic and medical information, laboratory data, electrocardiograms, and the results of any other tests or assessments. All information on CRFs must be traceable to these source documents in the patient's file. The investigator must also keep the original informed consent form signed by the patient (a signed copy is given to the patient).

The investigator must give the monitor access to all relevant source documents to confirm their consistency with the CRF entries. Novartis monitoring standards require full verification of the presence of informed consent, adherence to the inclusion/exclusion criteria,

documentation of SAEs, and of data that will be used for all primary variables. Additional checks of the consistency of the source data with the CRFs are performed according to the study-specific monitoring plan. No information in source documents about the identity of the patients will be disclosed.

8.2 Data collection

Designated investigator staff will enter the data required by the protocol into the Electronic Case Report Forms using fully validated software that conforms to 21 CFR Part 11 requirements. Designated investigator site staff will not be given access to the EDC system until they have been trained. Web based software will be used: no installation procedure will be needed. Each site will be authorized by the Administrator to access the eCRF. Each investigator site qualified personnel will be allowed to access the eCRF by means of a 'login mask' requiring User ID and Password and will be able to read, modify and update only the information he/she has previously reported. Each page should report site code and patient code. On-line validation programs check for data discrepancies and, by generating appropriate error messages, allow the data to be confirmed or corrected by the CRO working on behalf of Novartis. The Investigator must certify that the data entered into the Electronic Case Report Forms are complete and accurate. After database lock, the investigator will receive copies of the patient data on a CD-ROM for archiving at the investigational site.

8.3 Database management and quality control

CRO working on behalf of Novartis will review the data entered into the CRFs by investigational staff for completeness and accuracy and instruct the site personnel to make any required corrections or additions. The Data Manager of the CRO working on behalf of Novartis will perform the cleaning session reviewing the warning messages raised by on-line checks and running post-entry checks by means of validation programs. During this process, if clarifications are needed, the Data Manager will raise queries by means of data query forms through the WEB application. Designated investigator site staff is required to respond to the query and the Data Manager will make the correction to the database based on the query response. The data collection and the Queries flow as well as the on-line and off-line control checks will be detailed in the Data Management Plan and Data Validation documents.

Concomitant medications entered into the database will be coded using the WHO Drug Reference List, which employs the Anatomical Therapeutic Chemical classification system. Concomitant procedures, non-drug therapies and adverse events will be coded using the Medical dictionary for regulatory activities (MedDRA) terminology.

A central laboratory will analyze samples for Cw6 determination and enter the results in a dedicated section of the eCRF. Cohort status will be monitored to maintain the Cw6+/Cw6- ratio foreseen in the protocol.

Data about study drug will be tracked using the eCRF. The system will be supplied by a CRO, who will also manage the database.

The occurrence of any protocol deviations will be determined. After these actions have been completed and the database has been declared completed and accurate, it will be locked and made available for data analysis. Any changes to the database after that time can only be made

after written agreement between the Clinical Trial Leader, the Trial Statistician and the Data Manager.

8.4 Data Monitoring Committee

Not required.

8.5 Adjudication Committee

Not required.

9 Data analysis

All the data collected in this study will be listed and summarized as appropriate as described below. The data from all centers will be pooled and summarized. Continuous data will be summarized by mean, standard deviation (SD), median, first and third quartiles, minimum and maximum. Categorical data will be presented by absolute and relative frequencies (n and %).

Unless stated otherwise, two-sided p-values will be presented.

All statistical tables, listings and analyses will be produced using SAS® release 9.2 or later (SAS Institute Inc. Cary, NC, USA).

More details about data analysis will be provided in the Statistical Analysis Plan.

The data will be analyzed by the CRO working on behalf of Novartis.

9.1 Analysis sets

The following analysis populations will be defined for statistical analysis.

- Full Analysis Set (FAS): all enrolled patients.
- Safety: all enrolled patients who were given at least one dose of study drug.
- Intent-to-treat (ITT): all patients included in the safety population with at least one post-baseline efficacy assessment.
- Per-Protocol (PP): all patients included in the ITT population who completed the study without any major protocol violation.

The primary and secondary objectives will be evaluated on the ITT population. A supportive analysis will be done on the PP population.

All safety evaluations will be based on the safety population.

9.2 Patient demographics and other baseline characteristics

All data about patient demographics and baseline characteristics, including derived variables, will be summarized overall and by cohort with summary descriptive statistics. Continuous data will be summarized by mean, standard deviation, median, first and third quartiles, minimum and maximum. Categorical data will be presented by absolute and relative frequencies (n and %).

In order to interpret results adequately, the homogeneity of patient distribution between cohorts will be tested on selected baseline demographics and anamnestic variables (e.g. for gender, age, race, ethnicity, BMI, baseline PASI, baseline IGA, TNF α - 308 polymorphism, metabolic syndrome, smoking). Categorical variables will be analyzed by Cochran-Mantel-Haenszel test stratified by geographical region (i.e. north vs south/central) and BMI (< 25 vs \geq 25).

Continuous variables will be analyzed by means of ANOVA model corrected by geographical region and BMI classes, as appropriate. Statistically significant variables will be included as covariates in the explanatory analysis model. Whenever necessary, normality will be assessed by means of Shapiro-Wilk test and with graphical methods. In case of non-normality, a non-parametric test will be used.

The number of the analysis populations will be described and the reasons for excluding a patient from any particular population will be provided with the number of protocol violators for each criterion. The difference between cohorts with respect to protocol deviations and reasons for dropout will be examined.

Any condition entered as medical history or current medical conditions at baseline will be coded using the MedDRA dictionary. They will be summarized by system organ class and preferred term of the MedDRA dictionary.

Summaries of psoriasis-specific medical history will be provided as well.

9.3 Treatments

Study treatment administration details will be summarized overall and by cohort for the Safety population. The exposure to investigational drug (number of doses) and duration of exposure (days) will be summarized by means of usual descriptive statistics. Total actual dose will be compared with the total dose patients should take as per protocol and derived compliance will be summarized. The number of patients with permanent study drug interruptions will be described and the reasons that led to the interruption will be examined.

The use of rescue medication, concomitant medications and significant non-drug therapies will be summarized by Anatomic Therapeutic Chemical (ATC) class, overall and by cohort for the Safety population.

9.4 Analysis of the primary variable

The primary objective of this study is to evaluate the clinical response in Cw6-negative and Cw6-positive patients treated with secukinumab 300 mg with respect to the Psoriasis Area Severity Index (PASI) 90 response rate after 16 weeks, and thereafter for up to 72 weeks.

9.4.1 Variable

The primary efficacy variable is the PASI 90 response after 16 weeks of treatment, defined as the achievement of \geq 90% improvement (reduction) in PASI score after 16 weeks of treatment compared to baseline.

The primary analysis will be based on the ITT population. A supportive analysis will be performed on the PP population.

9.4.2 Statistical model, hypothesis, and method of analysis

The proportion of patients who reach PASI 90 at 16 weeks will be presented with the one-tailed 97.5% confidence interval of the Cw6 positive (POS) – Cw6 negative (NEG) difference.

The null hypothesis:

H0: Cw6 POS – Cw6 NEG \geq 0.12: The difference in proportion of subjects achieving PASI 90 response between the Cw6-positive cohort (Cw6 POS) and the Cw6-negative cohort (Cw6 NEG) is at least 12%.

The alternative hypothesis:

HA: Cw6 POS – Cw6 NEG $<$ 0.12: The difference in the proportion of subjects achieving PASI 90 response between the Cw6-positive cohort (Cw6 POS) and the Cw6-negative cohort (Cw6 NEG) is less than 12%.

A logistic regression analysis model will be also fitted, considering geographical region, BMI, smoking, metabolic syndrome, TNF α -308 polymorphism, as well as the clinically relevant baseline variables as strata factors.

9.4.3 Handling of missing values/censoring/discontinuations

All attempts will be made to ensure that the database contains full information for all data. For subjects who prematurely discontinue the study for any reason or subjects with missing visits (after baseline), PASI will be imputed using the Last Observation Carried Forward (LOCF) approach. If all PASI post-baseline efficacy values are missing, then these missing values will not be imputed and this subject will be removed from the analysis.

9.4.4 Supportive analyses

A sensitivity analysis on the primary efficacy variable will be performed considering the subjects who prematurely discontinued the study without a 16-week PASI assessment as non-responders.

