9.7 Sample size calculation

The primary objective of this study is to evaluate the clinical response in PASI 90 at week 16 of Cw6-negative and Cw6-positive psoriatic patients.

According to literature data, Cw6-positive patients will be about 60% of the entire psoriatic patient population.

From a previous study with ustekinumab (Talamonti et al. 2013) we can observe a difference in response to PASI 90 between Cw6-positive vs Cw6-negative patients of around 30%, in favor of Cw6-POS. Therefore, it is sensible to expect a response in the Cw6-negative cohort not less than 12 % respect to the Cw6-positive group. Further considerations are stated in the paragraph below.

Phase III data on secukinumab show a PASI 90 response at 16 weeks of 71%. Under the assumption that 60% of all the enrolled patient population is represented by Cw6-POS patients, we can reasonably assume to observe a proportion of patients with PASI 90 of 80% in the Cw6-POS cohort.

Under these assumptions, considering a one-side alpha level of 0.025 and a power of 80%, 365 patients (219 Cw6-POS and 146 Cw6-NEG) are sufficient to evaluate if the response in terms of PASI 90 in the Cw6-negative cohort is not less than 12% respect to the Cw6-positive cohort.

Considering a dropout rate at 16 weeks of 10% equally divided in the two studied cohorts, a total of 406 patients should be enrolled.

All calculations were done with NQuery 7.0.

A power analysis based on a different Cw6 patient distribution was made in order to facilitate patient enrollment without power-loss in the primary endpoint evaluation. Table 9-1 shows how the enrollment rate should be set free until the ratio between Cw6-POS and Cw6-NEG reaches the 1:1 rate-distribution, with a power of at least 80%.

In particular, the number of Cw6-POS evaluable patients will range from 219 to 182, whereas those in the Cw6-NEG cohort will range from 146 to 182.

Based on the table below, the enrollment in one of the two cohorts will be stopped when the target number is achieved (a maximum of 244 Cw6-POS patients will be allowed).

Table 9-1: Power analysis

Power	Ratio	Cw6 POS %	Cw6 NEG %	Cw6 POS N	Cw6 NEG N	Overall N	Drop out 10%	
							Cw6 POS N	Cw6 NEG N
80%	0,66	60%	40%	219	146	365	244	163
80%	0,70	59%	41%	215	150	365	239	167
80%	0,72	58%	42%	212	153	365	236	170
80%	0,75	57%	43%	209	156	365	233	174
81%	0,79	56%	44%	204	161	365	227	179
81%	0,82	55%	45%	200	165	365	223	184

81%	0,85	54%	46%	197	168	365	219	187

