2.5.2 Statistical hypothesis, model, and method of analysis

The proportion of patients who reach PASI 90 at 16 weeks will be presented with the one-tailed 97.5% confidence interval of the Cw6 positive (POS) – Cw6 negative (NEG) difference.

The null hypothesis:

H0: Cw6 POS - Cw6 NEG \ge 0.12: The difference in proportion of patients achieving PASI 90 response between the Cw6-positive cohort (Cw6 POS) and the Cw6-negative cohort (Cw6 NEG) is at least 12%.

The alternative hypothesis:

HA: Cw6 POS - Cw6 NEG < 0.12: The difference in the proportion of patients achieving PASI 90 response between the Cw6-positive cohort (Cw6 POS) and the Cw6-negative cohort (Cw6 NEG) is less than 12%.

The proportion of PASI 90 response by cohort as well as the difference between cohort together with 97.5% upper CI will be provided using Clopper Pearson CI method.

A logistic regression analysis model will also be fitted, considering age, geographical region (i.e. north vs south vs central), BMI categories (<25 vs >=25), waist circumference, smoking status (Yes vs No), metabolic syndrome (yes vs no), previous PsO therapy (naïve vs previous systemic therapy vs previous biologic therapy), PsA (yes vs no), age at diagnosis of psoriasis, TNF α -308 polymorphism, IGA mod 2011 (severe, moderate, mild) as strata factors.

Model selection:

If model does not converge due to particular covariate(/s), the corresponding covariate(/s) will be removed from the model using Stepwise selection method until model get converged.

Interpretation:

We can conclude that PASI 90 response in the Cw6-negative cohort is not less than 12% with respect to the Cw6-positive cohort if the upper bound of the 97.5 % CI of the difference (Cw6 POS - Cw6 NEG) is less than the non-inferiority margin of 12%.

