2.5.3 Handling of missing values/censoring/discontinuations

For patients who prematurely discontinue the study for any reason or patients with missing visits (after baseline), PASI will be imputed using the Last Observation Carried Forward (LOCF) approach. Additionaly non-responder imputation (NRI) analysis will be performed on primary endpoint (i.e., PASI 90 response with logistic regression analysis).

Non-responder imputation rule:

Non-responder imputation will be used: Missing values with respect to response variables based on PASI score will be imputed with non-response regardless to the reason for missing data (e.g. premature study discontinuation, missed visit, administrative issues), exceptions will apply to the following:

• If a subject dropped out the study prior to last scheduled visit and being responders consecutively at least for two preceding visits, the subject will be imputed as responder for the last scheduled visit.

• If a subject who was responder at visit x-1 and visit x+1 but has missing data at visit x, then the subject will be imputed for visit x.

The approach describes above will be adopted also for PASI 90 assessement reported in the extension phase.

The LOCF approach, as well as the NRI approach will be performed for drop-outs and patients with missing visits in between, however no imputation will be done on any visits for patients – entered in the extension phase **and** who have completed the study before reaching 72 weeks.

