2.5.4 Supportive analyses

A sensitivity analysis on the primary efficacy variable will be performed considering the patients who prematurely discontinued the study without a 16-week PASI assessment as non-responders. Hence, for this analysis non-responders patients are those who are PASI 90 responders who prematurely discontinued the study without a 16-week PASI assessment.

Summary of the number and percentage (n and %) of responders patients at week 16 will be presented by cohorts for this supportive analysis. Clopper Pearson confidence interval for a proportion will also be provided.

This supportive analysis will be done on the ITT set.

A supportive analysis on the primary efficacy variable will be also provided using prevalence approach (observed data) on ITT set and also using the PP set using both LOCF and NRI imputation method as well as prevalence approach.

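### The missing-data checks on the week-16 primary endpoint treat both cohorts alike; with similar drop-out, counting drop-outs as failures shrinks a real gap and is not a conservative test of the 12-point claim

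*Protocol*

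**What the plan says.** The null hypothesis in protocol 9.4.2 is that the difference in PASI 90 rate between the Cw6-positive cohort (POS) and "the Cw6-negative cohort (Cw6 NEG) is at least 12"%. SAP 2.5.2 concludes in favour of the claim if the upper bound of the 97.5% interval for POS − NEG "is less than the non-inferiority margin of 12"%.

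Missing week-16 data are handled as follows:

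- **Primary rule (protocol 9.4.3, SAP 2.5.3):** last observation carried forward (LOCF).
- **Sensitivity analysis (protocol 9.4.4, repeated in SAP 2.5.4):** "considering the subjects who prematurely discontinued the study without a 16-week PASI assessment as non-responders".
- **NRI (SAP 2.5.3), by logistic regression:** "Missing values with respect to response variables based on PASI score will be imputed with non-response regardless to the reason for missing data", with exceptions that count some drop-outs and some isolated missed visits as responders.
- **Observed data (SAP 2.5.4):** "A supportive analysis on the primary efficacy variable will be also provided using prevalence approach (observed data) on ITT set".
- **Per-protocol set (protocol 9.4.1, SAP 2.5.4):** in the SAP, with LOCF, NRI and observed data.

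Each of these applies the same rule to both cohorts. The multiple imputation in SAP 2.7.2 and 5.4.3 is for continuous PASI change and does not bear on the 12-point comparison. For the 9.4.4 analysis, SAP 2.5.4 names only counts, percentages and a Clopper-Pearson interval for a proportion. It names no interval for the difference.

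**The concern.** Counting drop-outs as failures is commonly taken to be the cautious choice. That is reasonable when the aim is to show that a difference exists. Here the aim is to show that a difference is smaller than 12 points, and the error to guard against is a real gap that looks too small. A rule that lowers both response rates in the same proportion also lowers the gap between them.

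If the LOCF result and the non-responder result agree, readers will take the claim to be robust to missing data. Where a real gap exists and drop-out is similar, that agreement is weaker evidence than it appears. No planned analysis asks how poorly the missing Cw6-negative patients would have to do, relative to the missing Cw6-positive patients, for the conclusion to change.

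**Working it through.** **Inputs.** One-sided alpha 0.025, 80% power and cohort sizes: "considering a one-side alpha level of 0.025 and a power of 80%, 365 patients (219 Cw6-POS and 146 Cw6-NEG) are sufficient" (protocol 9.7). Cw6-positive rate: "we can reasonably assume to observe a proportion of patients with PASI 90 of 80% in the Cw6-POS cohort" (protocol 9.7). Drop-out: "Considering a dropout rate at 16 weeks of 10% equally divided in the two studied cohorts" (protocol 9.7). Enrolled numbers 244 and 163: first row of Table 9-1. The Cw6-negative rate under the alternative is not stated; 80% is inferred from the expectation of no difference in protocol 1.1.

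**Reproducing the plan.** With an unpooled standard error, SE = √(0.80×0.20/219 + 0.80×0.20/146) = 0.0427. Power = Φ(0.12/0.0427 − 1.96) = 80.2%, which agrees with the plan and supports the inferred 80%. For enrolment, 365/0.9 = 405.6, rounded up to 406. By cohort, 219/0.9 and 146/0.9 round up to 244 and 163.

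**Effect of the non-responder rule.** If drop-out is unrelated to response, each rate p becomes p(1−d). With equal d the difference becomes (1−d)(p_POS − p_NEG). The chance of passing against 12 points is Φ((0.12 − difference)/SE − 1.96), with 244/163 patients.

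*True gap at the margin, 80% against 68%, 10% drop-out in each cohort:*

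- Rates: 0.80×0.9 = 72.0% and 0.68×0.9 = 61.2%, so the difference is 10.8 points.
- SE = √(0.72×0.28/244 + 0.612×0.388/163) = 0.0478.
- Chance of passing = Φ(0.012/0.0478 − 1.96) = 4.4%, against 2.5% nominal.
- The same steps give 3.4% at 5% drop-out and 7.0% at 20%.

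*Other true gaps, POS at 80%, 10% drop-out in each cohort (chance of passing):*

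| True gap (points) | Completers, 219/146 | Full data, 244/163 | Drop-outs as failures, 244/163 |
|---|---|---|---|
| 0 | 80.2% | 84.3% | 75.2% |
| 5 | 34.4% | 37.7% | 36.3% |
| 8 | 13.8% | 14.9% | 17.3% |
| 10 | 6.3% | 6.6% | 9.2% |
| 12 | 2.5% | 2.5% | 4.4% |

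With no gap there is nothing to shrink and the variance rises, so the check is harder to pass. The order reverses at a true gap of about 4 points against completers and about 6 points against full data.

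*Unequal drop-out at 80% against 68%:*

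- 12% POS, 8% NEG: 70.4% against 62.6%, difference 7.8 points, passes 13.8% of the time.
- 8% POS, 12% NEG: 73.6% against 59.8%, difference 13.8 points, passes 1.0% of the time.

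**What the symmetric rule does not show.** Suppose 80% respond in each cohort among those observed, with 10% missing in each. Drop-outs as failures in both cohorts gives an upper limit of 8.9 points, which passes. Now hold the missing POS patients at 80% and vary the missing NEG patients:

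- Missing NEG at 68%: NEG rate 0.9×80% + 0.1×68% = 78.8%, upper limit 9.2, passes.
- Missing NEG at about 42%: NEG rate 76.2%, upper limit about 12.0, the crossing point.
- Missing NEG all failures: NEG rate 72.0%, upper limit 16.5, fails.

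If, in addition, all missing POS patients are counted as responders, the rates are 82.0% and 72.0% and the upper limit is 18.4.

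**The case against.** A reader might infer that the 9.4.4 analysis cannot challenge the claim at all. The documents do not support that. A zero difference stays zero under equal drop-out while the interval widens. If Cw6-negative patients drop out more, the rule moves against the claim: with 80% responding in both cohorts among completers, 5% POS and 15% NEG drop-out gives an 8.0-point difference and an upper limit of 16.9.

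A reader might also infer that the check is generally easier to pass than the analysis it tests. That holds only for the larger true gaps. Near the decision limit it is slightly stricter: the largest completer-scale difference that still passes is 3.27 points, against 3.33 for completers and 3.76 for full data. The plan expects no gap and is powered on none.

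Nor do 4.4% or 13.8% describe the trial's type I error. The claim rests on the LOCF analysis, and the SAP does not set the 9.4.4 result against 12 points. The 13.8% case needs more drop-out among Cw6-positive patients. Nothing in the documents predicts that, since all patients receive the same regimen and both patients and investigators are blinded to Cw6, and its mirror case gives 1.0%.

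The plan is also broader than 9.4.4 alone. The observed-data analysis does not shrink the gap by (1−d), and the SAP's NRI exceptions mean it is not the pure failure rule modelled here. Missing data should be limited, because section 6 of the protocol asks patients who stop treatment to return for assessments, and the PASI 50 stopping rule acts only after the week-16 assessment.

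All of this stands and limits the size of the point. It does not supply an analysis that varies the assumption separately by cohort.

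**Conclusion.** The point holds as a gap in the sensitivity analyses. It is not an error in the primary test. Every planned missing-data analysis of the week-16 PASI 90 comparison uses one rule for both cohorts. Counting drop-outs as failures is a weak, non-conservative check of the 12-point claim when a real gap exists and drop-out is similar: 4.4% wrong passes at the margin instead of 2.5% at the plan's own 10% drop-out. Under unequal drop-out, whether the check is strict or lenient follows from which cohort happens to lose more patients (1.0% or 13.8% in the two mirror cases).

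These figures assume Wald intervals, the 244/163 split, drop-out unrelated to response, and a comparison of the check with 12 points. The unequal drop-out rates and the response rates given to missing patients are illustrative. Full data stands in for LOCF only if LOCF recovers true response status.

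**What to change.** In protocol 9.4.4 and SAP 2.5.4:

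1. Add a two-way tipping-point table for the week-16 difference. Vary the response rate assumed for missing Cw6-positive patients and, separately, for missing Cw6-negative patients, each from none to all responding. Report the 97.5% upper limit of POS − NEG for each combination and mark where it crosses 12 points.
2. For the existing non-responder analysis, also report the 97.5% upper limit of the difference.
3. State that symmetric non-responder imputation is not a conservative check for this hypothesis.

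The cost is one extra table from data already collected, with the primary analysis unchanged. The downside is that the result may look less robust.
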